Prior to leaving, patients will be given a sufficient supply of study medication (or placebo) to last until the next in-clinic visit at Visit 3 along with instructions for their use. Patients should be instructed to take their medication every morning thereafter at or around the same time.

If a titration dose is missed, or if 4 or more consecutive daily doses are missed during treatment, restart at last dose taken.

Telephone visits at Day 7,21,35,49,63,84,140,196,252, and 308 (± 7 days)

Telephone visits will be used between dose increases to monitor any safety events with participants. In addition, telephone visits will serve as safety check-in.

The following procedures will be performed at all scheduled telephone visits as shown in the schedule of events:

- Medication reconciliation
- AE assessment

Visit 3 at Day 14 (± 7 days) 0.50mg/day

The following tests and procedures will be completed in clinic:

- Concomitant medication reconciliation
- Labs (CBC w/ diff, CMP, TSH)
- EKG (pre-dose, post-dose at 6-hours ± 10 minutes)
- Vital signs including weight (pre-dose)
- Vital signs (post-dose every hour ± 10 minutes for 6 hours)
- Neuro and physical exam
- Blood biomarkers
- Dispense study drug and drug diary
- Drug accountability
- Adverse event assessment

Visit 4 at Day 28 (± 7 days) 0.75mg/day

The following tests and procedures will be completed in clinic:

- Concomitant medication reconciliation
- Labs (CBC w/ diff, CMP, TSH)
- EKG (pre-dose, post-dose at 6-hours ± 10 minutes)
- Vital signs including weight (pre-dose)
- Vital signs (post-dose every hour ± 10 minutes for 6 hours)
- Neuro and physical exam
- Blood biomarkers
- Dispense study drug and drug diary in clinic
- Drug accountability
- Adverse event assessment

Visit 5 at Day 42 (± 7 days) 1 mg/day

The following tests and procedures will be completed in clinic:

- Concomitant medication reconciliation
- Labs (CBC w/ diff, CMP, TSH)
- EKG (pre-dose, post-dose at 6-hours ± 10 minutes)
- Vital signs including weight (pre-dose)

- Vital signs (post-dose every hour \pm 10 minutes for 6 hours)
- Neuro and physical exam
- Blood biomarkers
- Dispense study drug and drug diary in clinic
- Drug accountability
- Adverse event assessment

Visit 6 at Day 56 (\pm 7 days) 1 mg/day

The following tests and procedures will be completed in clinic:

- Concomitant medication reconciliation
- Labs (CBC w/ diff, CMP, TSH)
- EKG
- Vital signs including weight
- Neuro and physical exam

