At the baseline visit (Visit 2), subjects who have met all the eligibility criteria for enrollment will be randomly assigned to one of two treatment groups:

1. Placebo (n=35) or
2. Siponimod 1 mg/day (n=70)

Randomization will be 2:1 and designed by our biostatistician. Randomization will take place during the Baseline visit.

In case of toxicity finding, the blinding will remain in effect as neither the Investigator, nor site staff will be informed whether the participants receive Siponimod or placebo. However, the study pharmacist will be informed in case there is need to adjust dosing if participants are treated with investigational product.

An independent statistician supporting the DSMB will be unblinded and may unblind the DSMB if required for proper study monitoring. All staff and research personnel involved in this study will remain blinded until all subjects have completed the trial and scientific data acquired.

STUDY INTERVENTION COMPLIANCE

Patient compliance with study medication will be assessed at each visit. Compliance will be assessed by direct questioning and counting returned tablets. Deviation(s) from the prescribed dosage regimen should be recorded in the CRF.

Patients who are significantly noncompliant will be instructed to discontinue medication from the study. A patient will be considered significantly noncompliant if he or she misses more than 21 consecutive days of study medication during the study without extenuating circumstance, for example: development of an SAE. Patients who stop dosing due to development of an SAE will have their case reviewed by investigator, site, medical monitor, DSMB, and Principal Investigator for prescribing appropriate actions. Similarly, a patient will be considered significantly noncompliant if he or she is judged by the investigator to have intentionally or repeatedly taken more than the prescribed amount of medication. Drug accountability will be emphasized at the start-up meeting, and drug accountability will be monitored throughout the study.

Temporary discontinuation of treatment with study drug due to ARIA-E should not be considered as non-compliance.

CONCOMITANT THERAPY

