A complete physical examination (with neurological exam) will be performed at the visits listed in the study protocol and schedule of events. An abbreviated physical examination, to include an ophthalmic examination and routine examination of the heart, lungs, abdomen, skin, and oral cavity, will also be performed. Sitting vital signs (blood pressure, heart rate, respiratory rate, and temperature), after each subject sits quietly for at least 5 minutes, and body weight will be assessed at the Screening Visit and at each subsequent visit.

+ Vital Signs

Body temperature (oral or tympanic) will be measured as specified in the Schedule of Activities and as clinically indicated.

Blood pressure and pulse rate (PR) will be measured as specified in the Schedule of Activities and as clinically indicated. Blood pressure and PR should be measured after at least 5 minutes of sitting.

+ Body Weight and Height

Body weight and height will be recorded as specified in the Schedule of Activities and as clinically indicated.

+ Neurological Examination

A directed neurological examination will be performed by the investigator at the time points specified in the protocol and schedule of events.

Any clinically significant change from baseline on follow-up physical/neurological examinations should be recorded as an AE and reported in the CRF. If additional ARIA-H, ARIA-E, are detected, an additional neurological exam may be performed by the investigator.

- Toxicity Assessment

During visits at the study site, we will collect blood samples and conduct blood counts and comprehensive metabolic panels to monitor hematologic and metabolic toxicities. All lab results will be reviewed by the primary investigator, or sub-investigators, to determine if any clinically significant findings are seen that could be attributed to Siponimod related toxicities.

- Procedure Used in Case of Toxicity

If toxicities are identified, we apply a special toxicity protocol. The hematologic or chemistry values indicative of severe AEs are those listed in exclusion criteria.

If toxicity, including cardiac SAEs, is suspected, or proven, to be linked to Siponimod, subjects will stop taking the study drug for 7 days, and undergo new blood tests after at least 7 days of washout. If test results continue showing toxicity, subjects will be withdrawn from the study and not replaced if this occurs after Visit 7.

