If toxicity markers improve, subjects will resume dosing at the prior lower dose (i.e., toxic dose minus 0.25 mg) and remain on this regimen until the end of the study. In case of a second toxic event, dosing will again be stopped for 7 days, and blood tests conducted. If the test results continue showing toxicity, subjects will be withdrawn and not replaced if this occurs after Visit 7. If toxicity markers improve, subjects will resume dosing at the previous lower dose (i.e., toxic dose minus 0.25 mg) and remain at this lower dose until the end of the study.

In case of a third toxic event, subjects will be withdrawn and not replaced if this occurs after Visit 7. When study medication is withdrawn, study subjects will be recorded as “End Of Study Drug Visit” and undergo the corresponding assessments (Week 52 in Table 1). Then, the subjects will be asked to complete the corresponding washout period schedule of assessments: (Week 56 in Table 1) and 26 week “End of Study” (Week 78 in Table 1).

- Tolerability Assessment

Tolerability of Siponimod in study subjects will be derived from the frequency of AEs and study withdrawal motivated by subjects’ discomfort during the dosing period.

- Standard MRI (screening 1)

Patients who do not have an MRI scan within the past 12 months of Screening Visit Day 1 will be scheduled for an vMRI or CT during the screening period with results obtained before randomization is decided. (MRI is preferred).

>> Routine MRI Scan (default choice)

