All SAEs (regardless of suspected causality) should be communicated within 24 hours of discovery of the event to the medical monitor and DSMB members, and to the local IRB within 10 working days.

Any SAEs occurring any time after study participation that are considered by the investigator to be possibly related to study drug must also be reported as outlined above.

The study site will be responsible for notifying the Food and Drug Administration (FDA) of any unexpected fatal or life-threatening suspected adverse reaction as soon as possible, but in no case later than 7 calendar days after the sponsor's initial receipt of the information. In addition, the site must notify FDA and all participating investigators in an Investigational New Drug (IND) safety report of potential serious risks, from clinical trials or any other source, as soon as possible, but in no case later than 15 calendar days after the sponsor determines that the information qualifies for reporting.

REPORTING EVENTS TO PARTICIPANTS

Participants will be informed to discontinue the study drug if blood or cardiac toxicity is discovered. The hematologic values indicative of severe AEs are those listed in exclusion criteria. Refer to section, Procedure Used in Case of Toxicity.

EVENTS OF SPECIAL INTEREST

Occurrences of acute overdose should be reported for tracking purposes. In this study, an overdose is defined as a dose greater than the specified dose and requires medical attention.

REPORTING OF PREGNANCY

Because Siponimod is a suspected teratogenic agent based on animal studies, females must be surgically sterile (bilateral tubal ligation, oophorectomy, or hysterectomy) or of non-childbearing potential.

Although it is currently unknown whether Siponimod present in semen can affect the growth of fetuses, male participants will be asked to use contraceptive methods preventing the exposure of fetuses to semen.

If, despite the use of contraceptives as described in this protocol, the partner of a subject becomes pregnant during the study, she will be followed through the end of her pregnancy. A Pregnancy Notification/Outcome Consent Form and Pregnancy Notification Form will be completed and faxed to the Drug Safety Department at Research Pharmaceutical Services Inc. (RPS). The outcome of the pregnancy and the medical condition of any resultant offspring will be reported on a Pregnancy Outcome Form.

UNANTICIPATED PROBLEMS

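### The stop-and-retest rule for toxicity covers cardiac events, but blood tests are the only retest it names for deciding between withdrawal and restart

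*Protocol*

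**What the plan says.** Section 10, Procedure Used in Case of Toxicity, opens its rule with a wide scope: "If toxicity, including cardiac SAEs, is suspected, or proven, to be linked to Siponimod". The action is that "subjects will stop taking the study drug for 7 days, and undergo new blood tests after at least 7 days of washout". The reference values are given one paragraph earlier: "The hematologic or chemistry values indicative of severe AEs are those listed in exclusion criteria".

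Two branches follow. Persisting toxicity on the retest leads to withdrawal. Otherwise, "If toxicity markers improve, subjects will resume dosing at the prior lower dose (i.e., toxic dose minus 0.25 mg", and the subject stays at that dose. A second event is handled in the same way: "In case of a second toxic event, dosing will again be stopped for 7 days, and blood tests conducted". A third event ends dosing.

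Section 11, Reporting Events to Participants, brings cardiac toxicity under the same procedure: "Participants will be informed to discontinue the study drug if blood or cardiac toxicity is discovered", with a cross-reference to the Section 10 procedure.

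Hepatotoxicity is outside this point, because Section 8 (Dosing and Administration) withdraws those subjects outright.

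**The concern.** The rule decides whether a subject is re-exposed after an adverse cardiac event. Section 3.1.1 lists bradycardia, bradyarrhythmia and AV conduction delay first among the potential serious events. The dose justification in Section 6 says there is no literature on cardiac events with siponimod in adults over 60. Safety is the primary objective.

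For this hazard the written test does not fit the event. A blood count or metabolic panel says nothing about heart rate, AV conduction or the QT interval. Two investigators who follow the text could reach opposite decisions on the same subject, because the text does not say what evidence of recovery is needed. At stake are subject safety and consistent handling of holds. This is a rule that the protocol itself fixes, not a detail that would be left to an analysis plan.

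**Working it through.** The protocol states no figure that bears on this point, so the check is a comparison of texts plus a little dose arithmetic.

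**1. What the retest can show.** The exclusion criteria that carry hematologic or chemistry values are lymphocytes or neutrophils below 1,000/mm³, platelets below 100,000/µL, transaminases above 2 times ULN and creatinine above 1.5 times ULN. None is a cardiac measure. The protocol does use cardiac signals elsewhere: a heart rate below 55 BPM during first-dose observation (Section 1.1) and QTc above 500 (Section 10, Electrocardiograms). The toxicity procedure refers to neither.

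**2. Running a cardiac event through the rule.** Suppose a subject has a symptomatic bradyarrhythmia with normal bloods.
- Dosing stops for 7 days and bloods are repeated. They are normal, as before.
- Withdrawal requires results that still show toxicity. The named test never showed any.
- Restart requires markers that have improved. The named test had nothing to improve.

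Neither branch clearly applies, and the same happens at a second event.

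**3. Whether other text supplies the cardiac retest.**

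| Provision | What it gives | Tied to restart? |
|---|---|---|
| Section 1.1, Unscheduled Visits | EKG, vital signs, examination, AE assessment | No; the procedure does not say that the retest is such a visit |
| Section 8, Study Intervention Compliance | Multi-party case review of SAE dosing stops | No resolution criterion; SAEs only |
| Section 9, Discontinuation of Study Intervention | Immediate notice to PI, medical monitor and DSMB | Notification only |
| Section 10, Safety Monitoring | Moderate to severe AEs go to medical monitor and DSMB | No |
| Section 10, Electrocardiograms | Investigator reviews EKG changes and decides on continuation | Triggered by an EKG change, not by the end of a hold |
| Section 11, follow-up and reporting | AEs followed to resolution; SAE course reported to DSMB | No |

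The visit schedule does not fill the gap by itself. Seven days after the titration visits at Days 14, 28 and 42 come Days 21, 35 and 49. These are telephone visits, limited to medication reconciliation and AE assessment.

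**4. Two side points on the restart dose.**
- *Missed-dose rule.* Section 1.1 says: "If a titration dose is missed, or if 4 or more consecutive daily doses are missed during treatment, restart at last dose taken". The hold is 7 days × 1 dose/day = 7 doses, and 7 ≥ 4. If held doses count as missed, both rules apply. For an event at 1.00 mg, the toxicity procedure gives 1.00 − 0.25 = 0.75 mg and the missed-dose rule gives 1.00 mg. The difference is 0.25 mg at every step. Neither rule mentions the other.
- *Lowest step.* For an event at 0.25 mg/day, 0.25 − 0.25 = 0, so no restart dose exists. The same happens at a second event after a first at 0.50 mg: 0.50 → 0.25 → 0. The procedure does not say that dosing then ends.

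**The case against.** The strongest reply is that the safeguards work without a cross-reference. On SAE stops, Section 8 says "Patients who stop dosing due to development of an SAE will have their case reviewed by investigator, site, medical monitor, DSMB, and Principal Investigator", which is a case-specific decision on the very cardiac SAEs that the rule names. Every scheduled clinic visit and every unscheduled visit includes an EKG, so a retest done in clinic would in practice produce one, and the investigator must review and document it. Also, the branch wording speaks of test results and toxicity markers in general, not of blood results alone.

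Much of this stands. A reader might infer that the protocol would restart a subject after a cardiac event with no cardiac assessment. The documents do not support that, because several parties would know of the event and an EKG would probably be on file. What remains is that none of these provisions makes cardiac or clinical resolution the condition for resuming, and the only test that the rule names cannot establish it.

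A reader might also infer that the missed-dose rule contradicts the toxicity procedure and sends subjects back to the dose that caused the event. That goes too far. The toxicity procedure is the specific rule for a protocol-ordered hold and states its own restart dose, so it would normally govern over a general instruction on missed doses. Section 8 does treat an SAE gap as missed medication, but only to exempt it from the noncompliance rule. The two rules overlap without stated precedence; they do not conflict.

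**Conclusion.** The point holds for the cardiac retest. A rule that expressly covers cardiac events names only blood tests, at both the first and the second event, and gives no clear decision when the bloods were never abnormal. The severity is minor to moderate, as safety wording. It does not alter any estimate, endpoint or analysis population as the protocol defines them. Anyone who took at least 1 dose stays in the safety analyses, so the triggering event is counted whichever branch is taken.

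The conclusion assumes that the procedure would be followed as written and that no operations manual (not available here) adds a cardiac retest. The protocol gives no expected number of toxicity holds, so no frequency is estimated. A reader might infer that all 105 planned subjects carry the drug-related heart-rate risk at the first dose step. It applies to the 70 assigned siponimod, although blinded holds could also involve some of the 35 on placebo.

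The missed-dose overlap and the 0.25 mg step are minor clarifications only. The latter errs on the safe side, since there is no dose left to resume.

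**What to change.** In Section 10, Procedure Used in Case of Toxicity, state for the first and the second event:
- After a cardiac event, the retest is an unscheduled visit as defined in Section 1.1, with EKG, vital signs and symptom assessment in addition to bloods.
- Dosing resumes only if these show resolution and, for an SAE, the Section 8 case review agrees. For a non-serious cardiac event, the investigator's continuation decision under Electrocardiograms applies.
- The sponsor and medical monitor set the clinical thresholds for resolution.

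Two optional clarifications:
- Add to the missed-dose instruction in Section 1.1 that it does not apply to toxicity holds, where the Section 10 procedure governs.
- State that an event at 0.25 mg/day ends dosing, because no lower dose exists.

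The cost is protocol wording. The assessments already belong to every unscheduled visit. The downside is slightly longer text and possibly a few more withdrawals after cardiac events; under the existing rule those after Visit 7 are not replaced.

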11. ADVERSE EVENTS AND SERIOUS ADVERSE EVENTS

DEFINITION OF ADVERSE EVENTS (AE)

An adverse event (AE) is any untoward medical occurrence in a clinical study participant administered pharmaceutical (investigational or non-investigational) product. An AE does not necessarily have causal relations with the intervention. An AE can therefore be any unfavorable and unintended sign (including an abnormal finding), symptom, or disease temporally associated with the use of a medicinal (investigational or non-investigational) product. (Definition per International Council on Harmonisation [ICH]).

This includes any occurrence that is new in onset or aggravated in severity or frequency from the baseline condition, or abnormal results of diagnostic procedures, including laboratory test abnormalities. The collections of AEs will begin at the Baseline visit after the first administration of study medication/placebo with the exception of study procedure related AE's that may occur during the screening process.

An unexpected adverse event is any AE, the specificity or severity of which is not consistent with the Investigator's Brochure.

A life-threatening adverse event is any AE that, in the view of the Investigator, places the subject at immediate risk of death from the reaction as it occurred. Disability is defined as a substantial disruption of a person's ability to conduct normal life functions.

DEFINITION OF SERIOUS ADVERSE EVENTS (SAE)

A serious adverse event is any AE that is fatal or life threatening (see below), results in persistent or significant disability (see below) or incapacity, requires inpatient hospitalization or prolongation of an existing hospitalization or is a congenital anomaly/birth defect or results in death. Other important medical events that may not result in death, be life threatening or require hospitalization should also be considered a serious adverse event when, based upon appropriate medical judgment, they may jeopardize the subject and may require medical or surgical intervention to prevent one of the outcomes listed above. Examples of such medical events include allergic bronchospasm requiring intensive treatment in an emergency room or at home, blood dyscrasias or convulsions that do not result in inpatient hospitalization, or the development of drug dependency or drug abuse. Associated with the use of the drug means that there is a reasonable possibility that the experience may have been caused by the drug.

An event is classified as serious if it meets any of the following criteria:

- Results in death.
- Is life-threatening.
- Requires inpatient hospitalization or prolongs an existing hospitalization.
- Results in persistent or significant disability/incapacity.
- Other important medical events. Medical and scientific judgment should determine whether an AE should be classified as serious in other situations, such as important medical events that may not be immediately life-threatening or result in death or hospitalization but may jeopardize the subject or require intervention to prevent one of the outcomes listed in the definition above.

CLASSIFICATION OF AN ADVERSE EVENT

SEVERITY OF EVENT

The following levels of severity will be used in the evaluation of adverse events in our clinical study:

- **Mild:** Awareness of symptoms that are easily tolerated, causing minimal discomfort and not interfering with everyday activities.
- **Moderate:** Sufficient discomfort is present to cause interference with normal activity.
- **Severe:** Extreme distress, causing significant impairment of functioning or incapacitation. Prevents normal everyday activities.

The investigator must use clinical judgement in assessing the severity of events not directly experienced by the participant (e.g. laboratory abnormalities).

RELATIONSHIP TO STUDY INTERVENTION

The following definitions of relationship to study drug will be used to characterize the suspected causality of each AE, based on the Investigator's consideration of all available information:

- **Related:** There is a reasonable causal relationship between study intervention administration and the AE.
- **Probably Related:** The relationship with the use of the study drug seems relevant and/or the event cannot be reasonably explained by another cause, but additional information may be obtained.
- **Possibly Related:** The relationship with the use of the study drug is weak but cannot be ruled out completely. Alternative causes are also possible (e.g., underlying or concurrent illness/clinical condition or/and an effect of another drug). Cases where relatedness cannot be assessed, or no information has been obtained should also be classified as possible.
- **Not Related:** No evidence that AE/SAE is related to the administration of the study drug.

An Emergency Code Break procedure will be available to the investigator to allow for unblinding of a patient, i.e. informing the investigator to which treatment group the patient has been assigned. Such procedures should only be utilized in emergency situations when the identity of the subject must be known by the investigator in order to provide appropriate medical treatment, i.e. unblinding is not required and should not be performed if knowledge of the patient's treatment group would have no influence on how the patient is being treated in the emergency situation.

EXPECTEDNESS

The Principal Investigator will be responsible for determining whether an adverse event (AE) is expected or unexpected. An AE will be considered unexpected if the nature, severity, or frequency of the event is not consistent with the risk information previously described for the study intervention.

TIME PERIOD AND FREQUENCY FOR EVENT ASSESSMENT AND FOLLOW-UP

The occurrence of an adverse event (AE) or serious adverse event (SAE) may come to the attention of study personnel during study visits and interviews of a study participant presenting for medical care, or upon review by a study monitor.

All AEs including local and systemic reactions not meeting the criteria for SAEs will be captured on the appropriate case report form (CRF). Information to be collected includes event description, time of onset, clinician's assessment of severity, relationship to study product (assessed only by those with the training and authority to make a diagnosis), and time of resolution/stabilization of the event. All AEs occurring while on study must be documented appropriately regardless of relationship. All AEs will be followed to adequate resolution.

Any medical condition that is present at the time that the participant is screened will be considered as baseline and not reported as an AE. However, if the study participant's condition deteriorates at any time during the study, it will be recorded as an AE.

Changes in the severity of an AE will be documented to allow an assessment of the duration of the event at each level of severity to be performed. AEs characterized as intermittent require documentation of onset and duration of each episode.

Study Coordinator will record all reportable events with start dates occurring after the first administration of study medication/placebo with the exception of study procedure related AE's that may occur during the screening process within 48 hours starting from when site became aware of AE and/or SAE. At each study visit, the investigator will inquire about the occurrence of AE/SAEs since the last visit. Events will be followed for outcome information until resolution or stabilization.

ADVERSE EVENT REPORTING

The condition of each study subject will be monitored throughout the study. Signs and symptoms of possible AEs may be observed by the staff, elicited by asking the patient and/or study partner/informant an open or indirect question (e.g. How have you felt since your last clinic visit?) or volunteered by the subject and/or study partner. All adverse events, whether observed by the investigator or staff, elicited from the subject or study partner, or volunteered by the subject or study partner, will be recorded in the

case report form. Data will include start and end dates, investigator-specified severity and relationship to study drug, and action taken. Whether the event resulted in death, required (or prolonged) hospitalization with persistent or significant disability/incapacity, required intervention to prevent any of the above outcomes, and/or whether it was reported as serious to the medical monitor, DSMB, IRB, and Study Sponsor will also be recorded.

Knowledge of a serious adverse event occurring or worsening in a study subject at any time during the trial must be reported by telephone within 24 hours (if physically possible) to the investigator who will immediately inform the medical monitor, DSMB and IRB in accordance with the IRB's specific requirements. Reports relative to the subject's subsequent course must be submitted to the DSMB until the event has subsided or, in the case of permanent impairment, until the condition stabilizes. At any time following the study, the investigator should immediately notify medical monitor, DSMB, and IRB if he learns of the occurrence of any malignancy or pregnancy involving the participant of a clinical trial, of any serious adverse event that could possibly be related to study drug, or of any congenital anomaly in an offspring of a participant.

SERIOUS ADVERSE EVENT REPORTING

All SAEs (regardless of suspected causality) should be communicated within 24 hours of discovery of the event to the medical monitor and DSMB members, and to the local IRB within 10 working days.

Any SAEs occurring any time after study participation that are considered by the investigator to be possibly related to study drug must also be reported as outlined above.

The study site will be responsible for notifying the Food and Drug Administration (FDA) of any unexpected fatal or life-threatening suspected adverse reaction as soon as possible, but in no case later than 7 calendar days after the sponsor's initial receipt of the information. In addition, the site must notify FDA and all participating investigators in an Investigational New Drug (IND) safety report of potential serious risks, from clinical trials or any other source, as soon as possible, but in no case later than 15 calendar days after the sponsor determines that the information qualifies for reporting.

REPORTING EVENTS TO PARTICIPANTS

Participants will be informed to discontinue the study drug if blood or cardiac toxicity is discovered. The hematologic values indicative of severe AEs are those listed in exclusion criteria. Refer to section, Procedure Used in Case of Toxicity.

EVENTS OF SPECIAL INTEREST

Occurrences of acute overdose should be reported for tracking purposes. In this study, an overdose is defined as a dose greater than the specified dose and requires medical attention.

REPORTING OF PREGNANCY

Because Siponimod is a suspected teratogenic agent based on animal studies, females must be surgically sterile (bilateral tubal ligation, oophorectomy, or hysterectomy) or of non-childbearing potential.

Although it is currently unknown whether Siponimod present in semen can affect the growth of fetuses, male participants will be asked to use contraceptive methods preventing the exposure of fetuses to semen.

If, despite the use of contraceptives as described in this protocol, the partner of a subject becomes pregnant during the study, she will be followed through the end of her pregnancy. A Pregnancy Notification/Outcome Consent Form and Pregnancy Notification Form will be completed and faxed to the Drug Safety Department at Research Pharmaceutical Services Inc. (RPS). The outcome of the pregnancy and the medical condition of any resultant offspring will be reported on a Pregnancy Outcome Form.

UNANTICIPATED PROBLEMS

The Office for Human Research Protections (OHRP) considers unanticipated problems involving risks to participants or others to include, in general, any incident, experience, or outcome that meets **all** of the following criteria:

- Unexpected in terms of nature, severity, or frequency given (a) the research procedures that are described in the protocol-related documents, such as the Institutional Review Board (IRB)-approved research protocol and informed consent document; and (b) the characteristics of the participant population being studied.
- Related or possibly related to participation in the research (“possibly related” means there is a reasonable possibility that the incident, experience, or outcome may have been caused by the procedures involved in the research); and
- Suggests that the research places participants or others at a greater risk of harm (including physical, psychological, economic, or social harm) than was previously known or recognized.

UNANTICIPATED PROBLEM REPORTING

The investigator will report unanticipated problems (UPs) to the reviewing Institutional Review Board (IRB), NIH, the NI and to the DSMB. The UP report will include the following information:

- Protocol identifying information: protocol title and number, PI’s name, and the IRB project number.
- A detailed description of the event, incident, experience, or outcome.
- An explanation of the basis for determining that the event, incident, experience, or outcome represents an UP.
- A description of any changes to the protocol or other corrective actions that have been taken or are proposed in response to the UP.

To satisfy the requirement for prompt reporting, UPs will be reported using the following timeline:

- A Major Protocol Deviation – a deviation, based on the clinical judgment of the PI or their designee, determined to significantly impact the scientific soundness of the research plan or suggest the research placed participants or others at a greater risk of harm (physical, psychological, economic, or social harm) not previously recognized. A major deviation meets all criteria for an UP involving risk. Major Protocol Deviations /UPs will be reported to local IRB within 10 days of investigator becoming aware. These will be reported to the DSMB and to the study sponsor within 24h of the investigator becoming aware of the event.
- Any other UP will be reported to the DSMB and to the study sponsor within 5 days of the investigator becoming aware of the problem. These UPs will be reported to the site’s Institute QA Monitor within 7 days, and to the local IRB at continuing renewal.

REPORTING UNANTICIPATED PROBLEMS TO PARTICIPANTS

The study site will report UPs to participants who are directly involved in the UP, or if the UP identifies risks that may impact their willingness to participate. Appropriate actions for the continuation or withdrawal from the study will be discussed with the involved participants.

